**CONFIDENTIAL**

Date: 16 July 2020  
 Version: 5.0  
 Status: Final  
 Page: 2 of 125

**Novo Nordisk**

## Protocol amendment summary of changes table

DOCUMENT HISTORY		
Document version	Date	Applicable in country(-ies) and/or site(s)
Protocol version 5.0	16 July 2020	All countries
Protocol version 4.0	16 March 2020	All countries
Protocol version 3.0	22 December 2017	All countries
Protocol version 2.0	28 August 2015	All countries
Original protocol version 1.0	30 April 2015	All countries

### **1. Protocol version 5 (16 July 2020)**

This amendment is considered to be non-substantial based on the criteria set forth in Article 10(a) of Directive 2001/20/EC of the European Parliament and the Council of the European Union.

### **2. Overall rationale for preparing protocol, version 5.0:**

The protocol is amended to align the number of subjects among protocol sections 1 (Summary), 6.1 (Number of subjects), 6.6 (Subject replacement) and 17.1 (Sample size calculation).

Protocol: Liraglutide  
 Trial ID: NN8022-4179  
 UTN: U1111-1162-7884  
 EudraCT no.: 2014-004415-37

**CONFIDENTIAL**

Date: 16 July 2020  
 Version: 5.0  
 Status: Final  
 Page: 3 of 125

**Novo Nordisk**

Section # and name	Description of change	Brief rationale
1 – Summary	
The number of subjects is updated as following:
 
 
• Approximately 57 subjects to be randomised, 33 in part A and 24 in part B
 
• Evaluable subjects part A: at least 28
 
• Evaluable subjects part B: at least 17
 
	To update protocol section 1 with the Paediatric Investigational Plan modification approved in 04-Dec-2019 and to provide a consistent accurate estimate of the number of randomised and evaluable subjects, across all protocol sections, as required by the Italian Health Authority
6.1 – Number of subjects	The number of subjects planned to be randomised is updated to 57 in total, divided into 33 for part A and 24 for part B. The number of maximum subjects to be randomised is removed.	To align the protocol section 6.1 – the number of planned randomised subjects – with the statistical calculation for sample size described in protocol section 17.1
6.6 – Subject replacement	
The split of the number of evaluable subjects per age group is updated as following:
 
 
• Part A: evaluable number of subjects is increased
 
• Part B: evaluable number of subjects is reduced
 
	To update protocol section 6.6 with the Paediatric Investigational Plan modification approved in 04-Dec-2019 and to provide a consistent accurate estimate of the number of evaluable subjects across all protocol sections, as required by the Italian Health Authority
17.1 – Sample size calculation	The planned number of randomised subjects is updated, as well as the respective treatment difference. Table 17-2 (Overview of randomised subjects) is also updated with more accurate numbers.	To update the protocol section 17.1 with the Paediatric Investigational Plan modification approved in 04-Dec-2019 and to provide a consistent accurate estimate of the number of randomised and evaluable subjects across all protocol sections, as required by the Italian Health Authority

Protocol: Liraglutide  
 Trial ID: NN8022-4179  
 UTN: U1111-1162-7884  
 EudraCT no.: 2014-004415-37

~~CONFIDENTIAL~~

Date:  
 Version:  
 Status:  
 Page:

16 July 2020  
 5.0  
 Final  
 4 of 125

**CONFIDENTIAL**

Date: 16 July 2020  
 Version: 5.0  
 Status: Final  
 Page: 5 of 125

**CONFIDENTIAL**

Date: 16 July 2020  
 Version: 5.0  
 Status: Final  
 Page: 6 of 125

**Novo Nordisk**

## List of abbreviations

ACTH	adrenocorticotrophic hormone
ADA	American Diabetes Association
AE	adverse event
ALT	alanine aminotransferase
ANCOVA	analysis of covariance
AST	aspartate aminotransferase
AUC	area under the curve
BG	blood glucose
BMI	body mass index
BOCF	baseline observation carried forward
CEA	carcinoembryonic antigen
CLAE	clinical laboratory adverse event
CL/F	apparent clearance
CPK	creatine kinase
CRF	case report form
C-SSRS	columbia suicidality severity rating scale
DHEAS	dehydroepiandrosterone sulfate
DMC	data monitoring committee
DUN	dispensing unit number
ECG	electrocardiogram
eCRF	electronic case report form
EOS	end-of-study
EOT	end-of-treatment
EMA	European Medicines Agency
FAS	full analysis set
FDA	Food and Drug Administration
FPFV	first patient first visit
FPG	fasting plasma glucose

Protocol: Liraglutide  
 Trial ID: NN8022-4179  
 UTN: U1111-1162-7884  
 EudraCT no.: 2014-004415-37

**CONFIDENTIAL**

Date:  
 Version:  
 Status:  
 Page:

16 July 2020  
 5.0  
 Final  
 10 of 125

**Novo Nordisk**

FSH	follicle stimulating hormone
FU	follow up
GCP	Good Clinical Practice
GH	Growth
GLP-1	glucagon-like peptide-1
HbA 1c	glycosylated haemoglobin
hCG	human chorionic gonadotrophin
HDL	high density lipoprotein
IB	Investigator's Brochure
hsCRP	high sensitivity C reactive protein
ICMJE	International Committee of Medical Journal Editors
IEC	independent ethics committee
IGF-1	insulin-like growth factor-1
IMP	investigational medicinal product
IRB	Institutional Review Board
ITT	intention-to-treat
IV/WRS	interactive voice/web response system
LAR	legally acceptable representative
LDL	low density lipoprotein
LH	luteinizing hormone
LOCF	last observation carried forward
LPFV	last patient first visit
LPLV	last patient last visit
MAP	modelling analysis plan
MedDRA	Medical Dictionary for Regulatory Activities
MHP	mental health professional
MESI	medical event of special interest
MI	multiple imputation
MMRM	mixed model for repeated measurements

Protocol: Liraglutide  
Trial ID: NN8022-4179  
UTN: U1111-1162-7884  
EudraCT no.: 2014-004415-37

~~CONFIDENTIAL~~

Date:  
Version:  
Status:  
Page:

16 July 2020  
5.0  
Final  
11 of 125

**Novo Nordisk**

MTD	maximum tolerated dose
NRS	numerical rating scale
PD	pharmacodynamic
PDCO	paediatric committee
PHQ-9	patient health questionnaire 9
PG	plasma glucose
PK	pharmacokinetics
PRO	patient reported outcome
PWS	Prader-Willi Syndrome
SAE	serious adverse event
s.c.	subcutaneous(ly)
SDS	standard deviation score
SDV	source data verification
SIF	safety information form
SMBG	self-measured blood glucose
SUSAR	suspected unexpected serious adverse reaction
T1DM	type 1 diabetes mellitus
T2DM	type 2 diabetes mellitus
TMM	trial materials manual
TPD	trial product discontinuation
TSH	thyroid stimulating hormone
UTN	universal trial number
V	visit
V/F	apparent distribution volume
WD	withdrawal

Protocol: Liraglutide  
Trial ID: NN8022-4179  
UTN: U1111-1162-7884  
EudraCT no.: 2014-004415-37

CONFIDENTIAL

Date: 16 July 2020  
Version: 5.0  
Status: Final  
Page: 12 of 125

Novo Nordisk

# 1 Summary

## Objectives and endpoints:

### Primary objective

To compare the efficacy of liraglutide versus placebo on weight loss in paediatric subjects with obesity and PWS at 16 weeks and versus no treatment at 52 weeks.

### Secondary objectives

- To compare the efficacy of liraglutide versus placebo on glycaemic control in children and adolescents with obesity and PWS at 16 weeks and versus no treatment at 52 weeks.
- To estimate the liraglutide steady state exposure in children and adolescents with obesity and PWS after 16 weeks of treatment.
- To compare the safety of liraglutide versus placebo in children and adolescents with obesity and PWS at 16 weeks and versus no treatment at 52 weeks.

### Primary endpoints

There are two co-primary endpoints:

- Change in body mass index (BMI) standard deviation score (SDS) from baseline to 16 weeks
- Change in body mass index (BMI) standard deviation score (SDS) from baseline to 52 weeks

### Key supportive secondary efficacy endpoints

- Percent of subjects achieving  $\geq 5\%$  reduction in baseline BMI at weeks 16 and 52
- Percent of subjects achieving  $\geq 10\%$  reduction in baseline BMI at weeks 16 and 52

Change from baseline to 16 and 52 weeks in:

- BMI
- Body weight (kilogram (kg), pounds (lb) and percent (%))
- Hyperphagia score:
  - total score and
  - hyperphagic behaviour, drive and severity score
- Systolic and diastolic blood pressure
- Glucose metabolism: glycosylated haemoglobin (HbA1c), fasting plasma glucose (FPG)

### Trial design:

This is a multi-centre, multi-national randomised, parallel group, placebo-controlled trial with a 16-week double-blind period and a 36-week open-label period. This trial consists of a part A and a part B. Part A of the trial is conducted in adolescents ( $\geq 12$  and  $< 18$  years, Tanner stage 2–5) with obesity and PWS. Part B of the trial is conducted in children ( $\geq 6$  and  $< 12$  years, Tanner stage

Protocol: Liraglutide  
 Trial ID: NN8022-4179  
 UTN: U1111-1162-7884  
 EudraCT no.: 2014-004415-37

~~CONFIDENTIAL~~

Date: 16 July 2020  
 Version: 5.0  
 Status: Final  
 Page: 13 of 125

**Novo Nordisk**

below 2 (defined as Tanner stage 1 with or without premature adrenarche)) with obesity and PWS. Entry into part A and part B of the trial will be sequential. The randomisation will be stratified according to pubertal status (part A) and by presence/absence of dysglycaemia (Parts A and B). After all subjects in part A have completed the 16 week double-blind period, an independent external Data Monitoring Committee (DMC) will review the PK data and safety data from part A. The DMC will recommend to the Novo Nordisk safety committee whether children in part B should be randomised, and exposed to liraglutide/liraglutide placebo. In addition, the tolerability/safety and PK data from trial NN8022-4181 in children with obesity 7-11 years (both inclusive) will be reviewed to allow adjustments in part B.

At least 30% of subjects will be from areas with lifestyle and nutrition comparable to that in the European Union (EU).

**Trial population:**

Approximately 57 subjects will be randomised 2:1 to receive liraglutide or liraglutide placebo. Approximately 33 subjects will be randomised in part A and 24 in part B.

The trial will continue until at least 45 evaluable subjects are included in total, divided as:

- Part A, at least 28 evaluable subjects
- Part B, at least 17 evaluable subjects
  - and of these subjects at least 5 need to be below 9 years of age.

**Key inclusion criteria:**

- Informed consent obtained before any trial-related activities. Trial-related activities are any procedures that are carried out as part of the trial, including activities to determine suitability for the trial
- Confirmed diagnosis of PWS (by genetic testing)
- Male or female, age at the time of signing informed consent:
  - Part A:  $\geq 12$  and  $< 18$  years
  - Part B:  $\geq 6$  and  $< 12$  years
- Tanner stage 2–5 pubertal development for part A, and Tanner stage below 2 (defined as Tanner stage 1 with or without premature adrenarche) for part B
- BMI corresponding to  $\geq 30 \text{ kg/m}^2$  for adults by international cut-off points and  $\geq$  the 95th percentile for age and sex (for diagnosis of obesity)
- Stable body weight during the previous 90 days before screening ( $< 10 \text{ kg}$  self-reported weight change)
- Testing has been performed to evaluate for adrenal insufficiency and documented in medical record

Protocol: Liraglutide  
Trial ID: NN8022-4179  
UTN: U1111-1162-7884  
EudraCT no.: 2014-004415-37

**CONFIDENTIAL**

Date: 16 July 2020  
Version: 5.0  
Status: Final  
Page: 14 of 125

**Novo Nordisk**

### **Key exclusion criteria**

- Type 1 diabetes mellitus (T1DM)
- Type 2 diabetes mellitus (T2DM)
- Calcitonin  $\geq 50$  ng/L
- No change in treatment plan with growth hormone (GH) from randomisation to the end of the open-label period (patients on growth hormone to stay on, patients off GH to stay off during this period. Adjustments in doses of growth hormone will be permitted)
- Family or personal history of Multiple Endocrine Neoplasia Type 2 (MEN2) or Medullary Thyroids Carcinoma (MTC)
- History of pancreatitis (acute or chronic)
- Treatment with any medication prescribed for weight loss within 90 days before screening (e.g. orlistat, zonisamide, topiramate/phentermine, lorcaserin, phentermine, bupropion/naltrexone, liraglutide, metformin)
- Untreated adrenal insufficiency
- Suggestive history of, or significant risk of gastroparesis (e.g. marked abdominal bloating post meal, history of vomiting, severe constipation), as judged by the Investigator

### **Assessments:**

#### **Efficacy**

- Height
- Body weight
- Hyperphagia questionnaire
- Systolic and diastolic blood pressure
- HbA1c and FPG

#### **Pharmacokinetic**

Area under the liraglutide plasma concentration - time curve (AUC)

#### **Safety**

- Adverse events
- Hypoglycaemia
- Anti-liraglutide antibodies

Protocol: Liraglutide  
Trial ID: NN8022-4179  
UTN: U1111-1162-7884  
EudraCT no.: 2014-004415-37

~~CONFIDENTIAL~~

Date:  
Version:  
Status:  
Page:

16 July 2020  
5.0  
Final  
15 of 125

**Novo Nordisk**

**Trial product(s):**

Liraglutide and liraglutide placebo are investigational trial products:

- Liraglutide 6.0 mg/ml, 3.0 ml, for s.c. injection with FlexPen®.
- Liraglutide placebo, 3.0 ml, for s.c. injection with FlexPen®.

## 2 Flow chart

Trial Periods	Screening	Screening	Randomisation	Dose escalation			Double blind treatment			Open-label treatment						End of treatment	Follow-up	TPD 16 week FU	TPD 52 week FU				
				4	5	6	7	8	9	10 	11	12 	13	14 	15 					16	17 	18 	
Visit number	1 	2 	3	4	5	6	7	8	9	10 	11	12 	13	14 	15 	16	17 	18 	19	20	10x	19x	
Timing of visit (weeks)	-2		0	1	2	3	4	8	12	16	20	24	28	32	36	40	44	48	52	54	16	52	
Visit window (days)				±2	±2	±2	±2	±5	±5	±5	±5	±5	±5	±5	±5	±5	±5	±5	±5	-5	±5	±5	
SUBJECT RELATED INFO/ASSESSMENTS																							
Informed consent and assents 18.2	x																						
In/exclusion criteria 6.2 6.3	x 	x	x																				
Discontinuation of trial product 6.4 8.1.8				x	x	x	x	x	x	x	x	x	x	x	x	x	x	x	x				
Withdrawal criteria 6.5				x	x	x	x	x	x	x	x	x	x	x	x	x	x	x	x				
8.1.9																							
Demography 8.3.1	x																						
Medical history and Concomitant illness  8.3.2		x																					
History of psychiatric disorders 8.3.2.1		x																					
Concomitant medication 8.3.3		x	x	x	x	x	x	x	x	x	x	x	x	x	x	x	x	x	x	x			
Tobacco use 8.3.4		x																					

Trial Periods	Screening	Screening	Randomisation	Dose escalation							Double blind treatment	Open-label treatment							End of treatment	Follow-up	TPD 16 week FU	TPD 52 week FU
				4	5	6	7	8	9	10 		11	12 	13	14 	15 	16	17 				
Visit number	1 	2 	3	4	5	6	7	8	9	10 	11	12 	13	14 	15 	16	17 	18 	19	20	10x	19x
Timing of visit (weeks)	-2		0	1	2	3	4	8	12	16	20	24	28	32	36	40	44	48	52	54	16	52
Visit window (days)				±2	±2	±2	±2	±5	±5	±5	±5	±5	±5	±5	±5	±5	±5	±5	±5	-5	±5	±5
Physical activity counselling 8.7.2.2			x	x	x	x	x	x 	x 	x	x 	x 	x 	x 	x 	x 	x 	x 	x	x	x	x
Dietary counselling 8.7.2.1			x	x	x	x	x	x 	x 	x	x 	x 	x 	x 	x 	x 	x 	x 	x	x	x	x
Dietary compliance 8.7.2.1				x	x	x	x	x 	x 	x	x 	x 	x 	x 	x 	x 	x 	x 	x	x		
EFFICACY																						
Body weight 8.4.1.1		x	x	x	x	x	x	x	x	x	x	x	x	x	x	x	x	x	x	x	x	x
Waist and hip circumference 8.4.1.2			x	x	x	x	x	x	x	x	x	x	x	x	x	x	x	x	x	x		
Hyperphagia questionnaire 8.4.2			x							x									x			
Systolic and diastolic blood pressure 8.4.3		x	x	x	x	x	x	x	x	x	x	x	x	x	x	x	x	x	x	x		
Lipids 8.4.4			x							x		x	x			x			x			
hsCRP 8.4.4			x							x			x			x			x			
Glucose metabolism 8.4.4		x	x							x		x	x			x			x			
SAFETY																						
Height 8.5.1		x	x							x		x				x			x		x	x
Adverse events 12		x	x	x	x	x	x	x	x	x	x	x	x	x	x	x	x	x	x	x	x	x
Hypoglycaemic episodes 8.5.2 and SMBG 8.5.2.1			x	x	x	x	x	x	x	x	x	x	x	x	x	x	x	x	x			

Trial Periods	Screening	Screening	Randomisation	Dose escalation			Double blind treatment	Open-label treatment										End of treatment	Follow-up	TPD 16 week FU	TPD 52 week FU	
				4	5	6		7	8	9	10 	11	12 	13	14 	15 	16					17 
Visit number	1 	2 	3	4	5	6	7	8	9	10 	11	12 	13	14 	15 	16	17 	18 	19	20	10x	19x
Timing of visit (weeks)	-2		0	1	2	3	4	8	12	16	20	24	28	32	36	40	44	48	52	54	16	52
Visit window (days)				±2	±2	±2	±2	±5	±5	±5	±5	±5	±5	±5	±5	±5	±5	±5	±5	-5	±5	±5
Pulse 8.5.3		x	x	x	x	x	x	x	x	x	x	x	x	x	x	x	x	x	x			
ECG 8.5.4		x								x									x			
Pregnancy test  8.5.5		x 	x	x	x	x	x	x	x	x	x	x	x	x	x	x	x	x	x 			
First day of menstrual period 8.5.5.3			x	x	x	x	x	x	x	x	x	x	x	x	x	x	x	x	x	x		
Physical examination 8.5.6		x											x			x			x			
Biochemistry 8.5.7		x											x			x			x			
Haematology 8.5.7		x											x			x			x			
Hormones  8.5.7			x										x			x			x			
Calcitonin 8.5.7		x											x			x			x			
Anti-liraglutide antibodies 8.5.8			x																x 	x 		
Tanner staging 8.5.9		x																	x 			
PHQ-9 and C-SSRS (part A only) 8.5.10		x																	x			
OTHER ASSESSMENTS																						
Liraglutide plasma concentration 8.7.1				x 	x 	x 		x 	x 	x 										x 		
TRIAL MATERIAL																						
Dispensing visit 9			x				x	x	x	x	x 	x 	x 	x 	x 	x 	x 	x 				
Drug accountability 9.4							x	x	x	x	x 	x 	x 	x 	x 	x 	x 	x 				

Trial Periods	Screening	Screening	Randomisation	Dose escalation			Double blind treatment	Open-label treatment								End of treatment	Follow-up	TPD 16 week FU	TPD 52 week FU			
				4	5	6		7	8	9	10 	11	12 	13	14 					15 	16	17 
Visit number	1 	2 	3	4	5	6	7	8	9	10 	11	12 	13	14 	15 	16	17 	18 	19	20	10x	19x
Timing of visit (weeks)	-2		0	1	2	3	4	8	12	16	20	24	28	32	36	40	44	48	52	54	16	52
Visit window (days)				±2	±2	±2	±2	±5	±5	±5	±5	±5	±5	±5	±5	±5	±5	±5	±5	-5	±5	±5
IV/IWRS session 10	x		x				x	x	x	x	x 	x 	x 	x 	x 	x 	x 	x 	x 			
New dose of trial product 8.1.7				x	x	x	x															
REMINDERS																						
Training in trial product & pen handling (including injection technique) 8.1.6			x	x	x	x	x	x	x	x	x 	x 	x 	x 	x 	x 	x 	x 				
Hand-out and instruct in BG meter 8.5.2.1			x																			
BG meter finger prick test 8.5.2.1			x	x	x	x	x	x	x	x	x	x	x	x	x	x	x	x	x			
Dispense dosing diary 8.7.3.1			x																			
Collect dosing diary				x	x	x		x	x	x												
Dispense hypoglycaemic episode diary 8.7.3.2			x																			
Collect hypoglycaemic episode diary				x	x	x	x	x	x	x	x	x	x	x	x	x	x	x	x			
Dispense menstrual period diary 8.7.3.3			x																			

Protocol: Liraglutide  
 Trial ID: NN8022-4179

UTN: U1111-1162-7884  
 EudraCT no.: 2014-004415-37

Date:  
 Version:

16 July 2020 | Status:  
 5.0 | Page:

Final  
 20 of 125 | **Novo Nordisk**

Trial Periods	Screening	Screening	Randomisation	Dose escalation			Double blind treatment			Open-label treatment						End of treatment	Follow-up	TPD 16 week FU	TPD 52 week FU			
				4	5	6	7	8	9	10 	11	12 	13	14 	15 					16	17 	18 
Visit number	1 	2 	3	4	5	6	7	8	9	10 	11	12 	13	14 	15 	16	17 	18 	19	20	10x	19x
Timing of visit (weeks)	-2		0	1	2	3	4	8	12	16	20	24	28	32	36	40	44	48	52	54	16	52
Visit window (days)				±2	±2	±2	±2	±5	±5	±5	±5	±5	±5	±5	±5	±5	±5	±5	±5	-5	±5	±5
Collect menstrual period diary				x	x	x	x	x	x	x	x	x	x	x	x	x	x	x	x	x		
Attend visit fasting 8.1.3		x	x							x						x			x	x 		

Abbreviation list: TPD = trial product discontinuation, FU = follow up, SMBG = self-measured blood glucose, PHQ-9 = Patient Health Questionnaire 9, C-SSRS = Columbia Suicidality Severity Rating Scale, V = visit, BG = blood glucose, IV/WRS = interactive voice/web response system, ECG = electrocardiogram, hsCRP = high sensitivity C reactive protein.

Protocol 4179-protocol-version-5.0.1  
 NN8022 -4179

Protocol: Liraglutide  
 Trial ID: NN8022-4179

UTN: U1111-1162-7884  
 EudraCT no.: 2014-004415-37

Date:  
 Version:

16 July 2020  
 5.0

Status: Final  
 Page: 21 of 125  
 Novo Nordisk

Footer	Description
1	Maximum two weeks between V1 and V3. V2 must be at least 1 day after V1, and V2 must be at least 5 days before V3, to ensure blood samples are available for randomisation.
2	All assessments at V10 should be performed prior to trial medication dispensing, as the trial medication dispensing session in IV/WRS as V10 will un-blind subject's treatment.
3	Home visits possible for subjects treated with liraglutide placebo only.
4	At V2 all pre-existing conditions should be reported as medical history or concomitant illness.
5	Visit can be performed as phone/video conference visit.
6	Only for females of childbearing potential. At V2 and V19 performed as serum pregnancy test and from V3-V18 urine-stick pregnancy test, if applicable 8.5.5 .
7	Estradiol for female subjects only and testosterone for male subjects only.
8	Subjects must be instructed to withhold their trial product dose until blood sampling is performed.
9	Only for subjects on open-label liraglutide treatment.
10	Tanner staging can be performed up to 2 weeks before V10 and V19.
11	No 8 hour fasting needed before V20. Minimum 2 hours after the last meal, the anti-liraglutide antibody sample at V20 is to be taken.
12	Please review inclusion criterion 7 and exclusion criterion 27 and evaluate whether a local testing for adrenal insufficiency is needed at V1

Protocol: Liraglutide  
Trial ID: NN8022-4179  
UTN: U1111-1162-7884  
EudraCT no.: 2014-004415-37

CONFIDENTIAL

Date: 16 July 2020  
Version: 5.0  
Status: Final  
Page: 22 of 125

Novo Nordisk

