**Novo Nordisk**

### **8.1.2 Visits attended fasting**

Fasting visits are specified in section [2](#). Fasting is defined as having consumed no food and drink except for water for the last 8 hours.

Any medication which should be taken with or after a meal should be withheld on the day of the visit until blood sampling and body weight measurements have been performed. Trial product can be taken as usual in relation to fasting visits.

In case a subject attends a fasting visit in a non-fasting state, all non-fasting measurements should be performed. The subject should return to the site in a fasting state to have fasting measurements done within the visit window for the relevant visit.

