**Novo Nordisk**

### 8.1.10 Home visits

Selected site visits as indicated in the flow chart (section [2](#)) can be converted to home visits during the open-label period for subjects in the liraglutide placebo group. The selected visits have no scheduled drug dispensing, blood sampling, ECG measurement, or physical examination.

Site staff must bring the following equipment during the home visit:

- Calibrated transportable scale
- Calibrated blood pressure monitor
- Measuring tape for measurement of waist and hips
- Urine sticks (applicable when females of childbearing potential are visited only)
- Equipment for pulse measurement
- BG meter for finger prick test (in case subject's own BG meter is not available)
- PHQ-9 questionnaire (self-completed by subjects)
- C-SSRS questionnaire:
  - questionnaire to be completed at home (if home visit is conducted by site staff certified as C-SSRS interviewer) or
  - set-up of telephone/video conference interview (if home visit is not conducted by site staff certified as C-SSRS interviewer)

Documentation for remaining assessments as per the flowchart (concomitant medication, adverse event, review and collection of menstrual information diary information etc.) must be obtained during the home visit. The site dietitian must be informed that the site visit is converted to a home visit so a telephone/video conference contact to the subject can be established.

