### 8.4.4 Blood samples for efficacy assessments

Any “abnormal, clinically significant” findings at V2 must be recorded as medical history/concomitant illness in the eCRF. The following blood samples must be drawn (for frequency see section [2](#)):

Lipids (fasting):

Protocol: Liraglutide  
Trial ID: NN8022-4179  
UTN: U1111-1162-7884  
EudraCT no.: 2014-004415-37

~~CONFIDENTIAL~~

Date: 16 July 2020  
Version: 5.0  
Status: Final  
Page: 51 of 125

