**Novo Nordisk**

- Total cholesterol
- LDL-cholesterol
- VLDL-cholesterol
- HDL-cholesterol
- Triglycerides
- Free fatty acids
- Non-HDL cholesterol

Biochemistry:

- High sensitivity C reactive protein (hsCRP)

Glucose metabolism:

- HbA1c
- FPG
- Fasting insulin
- Fasting C-peptide

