## Laboratory parameters

Summary statistics will be tabulated for each laboratory parameter. The distributions will also be presented graphically using box plots by treatment and week.

For each laboratory parameter, the values will be compared to the relevant reference range. The results will be presented as follows:

- Shifts from baseline at 16 and 52 weeks will be tabulated. The shift tables will include the number of subjects below, within and above the reference range at each visit
- The proportion of subjects with laboratory values outside the reference range will be tabulated per visit and treatment group
- Individual values outside the reference range (abnormal values) will be listed by treatment and subject

For amylase and lipase the relative change ( $100 \times \text{value}/\text{baseline}$ ) will be analysed with an MMRM model as described under sensitivity analysis in section [5.3.3](#). The response and baseline values will be log transformed prior to the analysis. Safety analysis set will be considered. All lab parameters will be reported in standard units. However for the parameters like Total Cholesterol, LDL, HDL, Triglycerides, Total bilirubin, Creatinine, calcium, HbA1C, Fasting plasma glucose conventional units will also be provided along with standard units in the descriptive statistics output.

Box plots will be provided for lab parameters like Calcitonin, Lipase, Amylase, ALT, AST and Prolactin

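### Week-28 (V13) lipid and glucose samples are defined as fasting, but the flow chart does not list V13 as a fasting visit, so their fasting status is not assured

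*Protocol*

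**What the plan says.** Protocol section 8.1.2 gives no list of fasting visits of its own. It says "Fasting visits are specified in section" 2, the flow chart, and sets the standard: "Fasting is defined as having consumed no food and drink except for water for the last 8 hours". It also has a recall rule: a child who arrives unfasted at a fasting visit should come back fasting within the visit window.

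In the flow chart, the row "Attend visit fasting" marks V2, V3, V10, V16, V19 and V20, with a footnoted 2-hour exception at V20. The V13 cell is empty. The rows for lipids and "Glucose metabolism" are both marked at V13.

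Section 8.4.4 heads the lipid list as fasting. Under glucose metabolism it lists HbA1c, FPG, "Fasting insulin" and fasting C-peptide. It takes the frequency of sampling from the flow chart.

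The SAP, under Laboratory parameters in section 5.4.1.3, plans by-visit output: "The proportion of subjects with laboratory values outside the reference range will be tabulated per visit and treatment group". The same subsection names total cholesterol, LDL, HDL, triglycerides and fasting plasma glucose among the parameters in the descriptive output.

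**The concern.** A site that follows the flow chart has no instruction to bring a child to V13 fasting, but is told to draw samples that the protocol calls fasting. Because V13 is not a listed fasting visit, the recall rule does not apply there either. Any mix of fasted and fed children would then be reported under fasting labels.

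Two uses are at stake. First, week-28 summaries and reference-range counts of FPG and lipids would stand beside values from weeks 16, 40 and 52, where fasting is required, with nothing to show the difference. Second, section 8.2 has results reported to investigators as they arrive, and section 8.2.2 requires each out-of-range value to be judged clinically significant or not. A glucose value labelled FPG but taken after food could mislead that judgement. V13 is also the first such draw after unblinding at week 16.

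**Working it through.** No power or alpha figure is involved. The check is an alignment of the schedule, a cross-check against the blood volumes, and a trace of where V13 values are used.

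**1. Flow-chart rows.** The chart has 22 visit columns (V1 to V20, 10x, 19x), and each row below resolves to 22 cells.

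| Row | Visits marked |
|---|---|
| Attend fasting | V2, V3, V10, V16, V19, V20 |
| Lipids | V3, V10, V12, V13, V16, V19 |
| Glucose metabolism | V2, V3, V10, V12, V13, V16, V19 |
| hsCRP | V3, V10, V13, V16, V19 |

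The lipid and glucose visits without a fasting mark are V12 and V13.

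**2. Is the V13 draw real?** The Table 8-1 volumes reproduce the stated total: 7.5 + 23.0 + 5 × 2.0 + 29.0 + 22.0 + 22.0 + 27.0 + 7.0 = 147.5 mL. V13 and V16 each have 22.0 mL. The same blood rows are marked at both visits: lipids, hsCRP, glucose metabolism, biochemistry, haematology, hormones and calcitonin. So the V13 panel is intended and matches that of a listed fasting visit. V12 has no volume in Table 8-1. It is also open to placebo home visits, of which section 8.1.10 says "The selected visits have no scheduled drug dispensing, blood sampling, ECG measurement, or physical examination". The V12 marks therefore carry no weight here.

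**3. Does any other text make V13 fasting?** Section 8.1 tells sites to hold visits according to the flow chart. Section 8.4.1.1 has weight at visits outside the fasting list measured unfasted. Only the sample names in section 8.4.4 point towards a fast at V13.

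**4. How reliable is a blank cell in this chart?** Take the liraglutide concentration sample as 2.0 mL (V4 to V6) and the antibody sample as 7.0 − 2.0 = 5.0 mL (V20). The V19 volume agrees: 22.0 + 5.0 = 27.0 mL. At V10, 2.0 + 5.0 + 22.0 = 29.0 mL, exactly the tabulated volume. V10 was therefore sized for the full panel plus antibodies, yet the biochemistry, haematology, hormone, calcitonin and antibody rows show no V10 mark. The Tanner row also lacks V10, although section 8.5.9 refers to it, and the PHQ-9/C-SSRS row lacks it although week-16 shifts are planned in section 17.4.1.2. Height is marked at V12, where SAP Table 6-3 has V13.

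**5. Where V13 values go.** SAP section 6.3.2.1 places the primary and secondary endpoint analyses at V10 and V19. Protocol section 17.4.1.1 tests lipids and glucose parameters as changes at weeks 16 and 52, and the imputation uses values at those two visits. Both are marked fasting.

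**6. Share of the schedule.** Among visits with a volume in Table 8-1, V13 is one of five lipid draws (V3, V10, V13, V16, V19), one of six glucose draws (those five plus V2), and one of three draws of each in the open-label period (V13, V16, V19).

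**The case against.** The strongest objection is that the missing V13 mark may not be missing from the protocol. Seven rows lack a V10 mark that other text or the blood volumes call for, and the height mark appears moved from V13 to V12. One more lost mark, in the fasting row, would fit that pattern. Table 8-1 supports the draw at V13; it cannot show that the fasting cell is truly empty. This stands, and it is why the first action is to look at the original chart.

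A reader might infer that the week-28 values come from fed children, in every subject. The documents do not support that. Section 8.4.4 still calls the samples fasting, some children may have attended fasted, and actual status at V13 is not reported. What follows is only that fasting is not assured.

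A reader might also infer that a false FPG would lead to a diabetes diagnosis and metformin, and so disturb the week-52 comparison. That is speculative. Nothing in the documents rests a diagnosis on one glucose value, HbA1c needs no fast and is in the same panel, and section 5.3.3 leaves metformin to the investigator once T2DM has developed. The documents give no fed-fasted difference from which to size such an effect.

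Finally, the affected output is narrower than it may appear. Shifts from baseline are planned at weeks 16 and 52, although the shift tables are also described as counting subjects at each visit. The box plots that the SAP names are for calcitonin, lipase, amylase, ALT, AST and prolactin, none of them in the fasting panel. Insulin, C-peptide and HOMA are not named under Laboratory parameters, so whether they appear by visit depends on output specifications outside these documents.

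**Conclusion.** As the flow chart reads, the protocol contradicts itself at V13: the samples are defined as fasting, and the visit is not. Neither the fast nor the recall of an unfasted child is assured. The consequence is confined to week-28 descriptive summaries and reference-range counts of FPG and lipids (and of insulin, C-peptide and HOMA if they are summarised by visit), and to investigator review of those results. The co-primary analyses and the week 16 and week 52 tests of lipids and glucose parameters are not directly affected.

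This rests on one assumption, that the V13 fasting cell is blank in the original document. If it is marked there, the point falls away. The number of non-fasting V13 samples, and the size of any distortion, cannot be derived from the documents.

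**What to change.** - Check the V13 cell of the fasting row in the original flow chart. In the same pass, check the V12 marks for lipids and glucose metabolism against Table 8-1 and section 8.1.10.
- If V13 is blank, reconcile the fasting row with the lipid and glucose rows and section 8.4.4 by marking V13 as fasting. The recall rule in section 8.1.2 then applies to it.
- For V13 samples already taken, flag each by actual fasting status. Where that was not recorded, label it unknown.
- State in the SAP that non-fasting V13 values of FPG, insulin, C-peptide, HOMA and lipids are left out of the fasting by-visit summaries and reference-range counts. HbA1c can stay.

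The cost is one flow-chart mark, one data flag and one more fasting morning per child. A side effect is that section 8.4.1.1 would then require V13 weight to be measured fasting.
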